## 2.4 Incisional hernia prevention

European Hernia Society (EHS) guideline strongly recommends to utilise a non-midline approach to a laparotomy whenever possible to decrease the incidence of incisional hernia (14). However, this is clearly not an option in an emergency laparotomy, as midline incision is the fastest and the best visualizing opening to explore the whole abdominal cavity in an emergency setting.

For elective midline incisions, evidence-based recommendation is to perform a continuous suturing technique with slowly absorbable monofilament suture when closing the incision (14) Suturation should be done performing a single layer aponeurotic closure technique without separate closure of the peritoneum. A small bites technique with a suture to wound length (SL/WL) ratio at least 4:1 is the current recommended method of fascial closure (12-14, 37,38).

Prophylactic mesh augmentation in a non-emergency setting appears effective and safe and

can be suggested for high-risk patients (39-40). However, no recommendations can be given on the optimal

PREEMER TRIAL 10

technique to close emergency laparotomy incisions because of lack of evidence (14) . This problem should be emphasized on due to high rates of IH after emergency laparotomy (41,42). All this makes the use of prophylactic mesh in the emergency setting an interesting proposition, as it may decrease the rate of IHs. However, there are concerns over potential mesh related complications including infection, chronic pain, seromas and bowel fistulas especially in emergency situations like peritonitis and intestinal obstruction. There is preliminary evidence published about the safety and efficiency of the prevention of IHs using meshes in the emergency laparotomy closure even in contaminated conditions (43,44).

In the resent systematic review and meta-analysis, only results of 2 studies and altogether 299 patients were eligible for the analysis (42) . Swiss case-control study reported an IH rate of 3,2% (2/63) in the mesh group and 28,6% (20/70) in the control group (43) . Spanish study group had the same kind of results in their retrospective cohort; IH rate of 5,9% (3/50) in the mesh group and 33,3% (33/100) in the control group (44) . There was no statistically significant difference in the incidence of surgical site infection or other complications when prophylactic mesh group was compared to standard closure group. SSI rate in Swiss study was 60% and respectively only 17% in the Spanish study. This may reflect differences in the patient selection, therefore the safety profile of the prophylactic mesh in the emergency setting has not been adequately described. Neither of the studies included in meta-analysis were not randomized controlled trials. There were also many methodological differences including patient selection, used mesh, and mesh placement. Thus, the conclusion of the systematic review paper was that there are limited data to assess the effect or safety of the use of prophylactic mesh in the emergency laparotomy setting (42) . Randomized control trials are required to address this important clinical question. EHS guideline group resulted the same conclusion in their recommendation report (14).

There are about 1650 patients are operated in Finland because of IH every year. According to the European study, the estimated cost for IH surgery is 6450 euros (45). The corresponding costs in Sweden were even higher reaching 9060 euros per treatment (12). Extrapolated to Finland, this means that operative treatment of IHs cause more than 10 million expenses to the Finnish health care sector in a year. Some of these costs may be avoidable by using the prophylactic mesh during the

closure of midline emergency laparotomies in the patients with IH risk factors.

PREEMER TRIAL 11

Therefore, our study group stands on the idea to design and carry out the PREEMER randomized controlled trial (RCT) comparing prophylactic mesh to best standard suturing technique in this challenging setting.

### 3. Study Objective

The objective of this study is to compare prospectively the feasibility and the potential benefits of retrorectus self-gripping mesh (Progrip™, Medtronic) to controls operated with no mesh by using the best standard 4:1 small stitch suturing technique.

### 4. Study Design

This study is a multicenter, double-blinded, randomized controlled trial. Parameters will be collected prospectively after randomization. All enrolled subjects will undergo assessments at the following intervals: pre-operative, operative, discharge, 30 days, 2- and 5-years post-surgery. A

description of the study visits and required study procedures is summarized in Section 12, Schedule of events.

All patients are evaluated both clinically and radiologically at 2 years after index procedure in

order to diagnose clinical and/or radiological incisional hernia. The follow up will continue until 5 years after the surgery to assess long-term results and safety.

Ultrasound with and without Valsalva maneuver will be performed to all patients 2 years after

surgery. The extent of the fascial defect and hernia sac volume (ie. the volume of incisional hernia) are measured and graded according to the European hernia society criteria. (46)

If there is a suspicion of symptomatic or asymptomatic incisional hernia according to clinical

assessment and ultrasound findings are inconclusive, CT scan is required to verify the diagnosis of IH. If a patient have had no imaging done for any reason, the result of clinical

evaluation is

recorded. In case of several imaging modalities accomplished, all results are recorded. All study

PREEMER TRIAL 12

patients are guided to contact their study site in case of any suspicion of incisional hernia at any point during follow up.

Quality of life will be measured using RAND-36, Activities Assessment Scale (AAS) and PROMIS questionnaire at all follow-up visits at 1 months, 2 years and 5 years as well as when a hernia is diagnosed.

## 5. Cost analysis

Costs of the treatment

- Mesh and other materials used to close the abdomen
- Need for further surgery and medical treatment
  - All complications of primary surgery
  - Mesh-related need for surgery or other treatment
  - Hernia-related need for surgery or any help from medical system
  - Length of sick leave
  - Need for rehabilitation before returning to previous place of home
  - Length of stay in the hospital

for both groups will be analyzed in detail.

## 6. Study Endpoints

### 6.1 Primary Endpoints

The primary endpoint of this study is the incidence of incisional hernia, either symptomatic or asymptomatic detected clinically and/or radiologically within 2 years after surgery.

In case of inconsistency between clinical and radiological evaluation exists or either one is missing for any reason, a following definition of primary endpoint will be used:

Clinical exam result	Imaging result	Primary endpoint
Hernia	Hernia	Hernia

No hernia	Hernia	Hernia
Hernia	No hernia	No hernia
No hernia	No hernia	No hernia
Hernia	Missing	Hernia
No hernia	Missing	No hernia
Missing	Hernia	Hernia
Missing	No hernia	No hernia

If there is inconsistency between ultrasound and CT scan, the result of CT scan will be applied.

## 6.2 Secondary Endpoints

Secondary Endpoints:

- Comprehensive Complication Index within 30 days from surgery
- Surgical site infection (SSI) rate defined by CDC classification of surgical site infection  
within 30 days follow up
- Fascial rupture within 30 days from surgery
- Incidence of Incisional hernia within 5 years follow-up
- Incisional hernia repair rate within 2 and 5 years after surgery
- Re-operations due to mesh- or hernia within 2 and 5 years from surgery
- Quality of life (RAND-36, AAS, PROMIS) within 30 days, 2 and 5 years from surgery
- Medico-economic explorative measures
  - Time to create the retrorectal space and insert the mesh
  - Length of stay
  - Costs of materials used to close the abdomen
  - Length of sick leave

## 7. Study Population

Eligible patients will be recruited at the approved participating sites. All patients who are eligible, meet the inclusion and none of the exclusion criteria of this study, will be offered enrolment into the study at each study site. A screening log of all gastrointestinal emergency midline laparotomies during study period will be maintained for further assessment of selection biases.

The following patient inclusion/exclusion criteria will be required for the study.

### 7.1. Inclusion Criteria

- Midline emergency laparotomy for any gastrointestinal indication
  - **Conversion from laparoscopy to laparotomy is considered as inclusion criteria from Study protocol version 3.0 onwards.**

### 7.2 Exclusion Criteria

- Previous ventral hernia repair with mesh in the midline
  - Previous inguinal or femoral hernia repair by any technique with mesh is accepted
- Previous WHO class of physical activity 3-4 (WHO 3 more than 50% of time at rest, WHO 4 stays at rest most of the time)
- Relaparotomy
- Indication for laparotomy is incarcerated hernia
- Pregnant or suspected pregnancy
- <18 years
- Metastatic malignancy of any origin
- Planned Ostomy
- Patients living geographically distant and/or unwilling to return for follow-ups
- No informed consent
- Subject participates in another RCT

Intra-operative exclusion criteria applicable for both randomization groups

- Abdomen is left open
- Second look laparotomy planned
- Inability to keep the mesh securely out of the peritoneal cavity or close the anterior fascia
- Intra-abdominal malignancy diagnosed at the operation
- >2 cm hernia in midline
- Ostomy made at the operation

## 8. Center and Surgeon Selection

Participating investigators are qualified surgeons experienced with surgical emergency management of patients with emergency midline laparotomy and centers have a patient population large enough fitting the study requirements. All surgeons considered for participation must be experienced in closing the abdomen by 4:1 small stitch technique and prophylactic self-

gripping polyester mesh (Progrip™) placement. A detailed brochure with step-by-step pictures of midline laparotomy closure and mesh application will be delivered to each participating hospital. Principal investigator may advise with mesh application technique if desired.

Hospitals located in Finland are considered for participation.

## 9. Risk Analysis

### 9.1. Potential Risks

Surgeons performing emergency laparotomies will be trained and guided for the mesh placement. Based on previous studies, the use of the mesh is both safe and effective.

Study patients will be

followed very closely postoperatively.

As the previous research on synthetic mesh utilized as prophylaxis at emergency midline laparotomy is scarce, an analysis of the complications and risks is done and evaluated for safety

reasons after 30 patients have been randomized to each group and reached 30 days follow-up. For the same reason, there will be further analysis on the complications of the mesh after 30 patients randomized to each group have reached the 2 years follow-up.

If there are significantly more-serious complications in either group compared to other at 30 days or 2 years control, the trial will be discontinued.

### 9.2. Potential Benefits

There may be some benefit due to trial-related closer follow-up of patients. Patients with a prophylactic mesh might have a lower incisional hernia rate.

## 10. Study Methods

### 10.1. Ethics Committee Approval

[figure not shown]
The study protocol, patient informed consent form and other required study documentation will be reviewed and approved by an ethics committee in Oulu University hospital and any other required body, prior to study start-up.

### 10.2. Study Duration and Enrollment

Study enrolment will take approximately 24 months. The enrolled patients will have a short-term follow-up at 30 days and, long-term follow-up at 2 and 5 years.

### 10.3. Study Plan

[figure not shown]
*Figure 1 Flow Chart*

Intend to treat population  
reaching 30 days control

Intent to treat  
population  
reaching 2 years  
control

Intent to treat  
population  
reaching 5 years  
control

Data will be collected at baseline, operative procedure, discharge, 30 days, 2 years and 5 years. Specific databases (Hoitoilmoitusrekisteri HILMO, Tilastokeskus) may be used to collect data of patients' survival and operations done to patient outside study sites. If there is any suspicion of

PREEMER TRIAL 17

incisional hernia raised at any point of the follow-up, the patient is advised to contact the study site and additional clinical evaluation and ultrasonography if needed is arranged. The data will be collected using electronical CRFs and software designed for this study.

### 10.1 Patient Informed Consent

Using the study-specific, ethics committee approved, informed consent form, information pertinent to this study will be provided to the subjects and/or representative in writing and using non-technical language. The consent form will include a description of the study and its purpose,

potential benefits, potential risks, site contact information, and all other elements required of an informed consent.

Subjects are required to voluntarily sign the informed consent form before any study-specific

procedure is performed. The Investigator will conduct the informed consent process and will answer questions the subjects may have. If the subject agrees to participate, the informed-consent form must be signed and dated by the subject prior to enrolment in the study and separately signed and dated by the investigator taking consent. Only subjects who have signed the study informed consent will be included in the study.

### 10.2 Data Collection

Following information of patients will be collected using electronic database. The patient is pseudonymized for data collection and all data will be handled using study-ID.

#### Baseline

- Age
- BMI
- Charlson Comorbidity Index
- Previous surgical history of abdomen
- History of smoking
- Previous hernias
- Previous hernia-related operations
- Previous WHO scale

- Medications affecting healing

- Corticosteroids
- Immunosuppressive medications
- Biologics
- Creatinine
- INR

## Operative Procedure

- Prophylactic antibiotics
- ASA
- Presence of hernias in midline
- Presence and width of rectus diastasis
- Contamination class
- Surgical procedure
- ICD-10
- Loss of blood
- Time to create the retrorectal space and insert the mesh
- Length of wound
- Suture material and needle used
- Drains left
- Vacuum assisted closure/other temporary closure/skin left
- open • Skin closure

## Primary hospital stay and Discharge

- Surgical site infection (SSI) rate
- All complications during hospital stay Comprehensive Complication Index

- Re-operations
- Burst abdomen
- Fascial dehiscence
- Length of stay (LoS)
- Mesh removals

- Place of discharge

Patients are guided to contact their study site in case of any problems with their recovery, any suspicion of hernia occurrence or wound complications.

### 30 days visit

The recovery of all patients is assessed at 30 days after the operation. All the patients are called to. If there are any deviations in recovery, patient is invited to outpatient clinic for follow-up visit.

- Date of return to previous home unit
- Return to previous level of activity
- Return to work, length of sick leave
- Bulging
- Wound status
- Any complications of recovery
- Re-admissions
- Re-operations
- Removal of mesh
- Quality of life (RAND-36, AAS, PROMIS)
- Protocol deviations

### 2 years Visit

Patient related recovery outcomes and QoL questionnaires will be completed and any complications, clinical signs and/or abdominal ultrasound findings of incisional hernia or protocol deviations will be reported. Both the patient and the surgeon assessing the recovery and well-being are blinded of the randomization group.

Ultrasound findings will all be analyzed by single independent radiologist in each study site, blinded of the randomization group. Possible hernia opening, its size, location and

incisional

hernia sack volume will be defined both at rest and with Valsalva maneuver. If the findings are

PREEMER TRIAL 20

inconclusive or there is discrepancy between the clinical assessment and imaging or a patient has a symptomatic incisional hernia and operative treatment is indicated, abdominal CT scan will be done to verify the hernia diagnosis or to plan operative technique.

## 5 years visit

Patient related functional outcome and QoL shall be completed and any complications, clinical signs of incisional hernia or protocol deviations are reported. Ultrasound scan will be done

following the same protocol as described at 2 years control if there is any suspicion of incisional hernia.

## 10.3 Blinding

Study patients will be blinded of the randomization group during the whole follow-up period.

Both the surgeon evaluating the outcome at 30 days, 2- and 5- years control as well as radiologist will

be blinded of the randomization group. The method of fascial closure (i.e. the allocated procedure) will not be revealed in medical records. In both groups, the following sentence will be

written in the medical records: "Fascial closure was performed according to randomization group". Patients randomization number will be available in medical records. Envelopes marked with randomization number containing allocated group information are accessible at all times in

case of complications or other need to know the allocated group. A record of unsuccessful blinding will be maintained and published.

## 11. Definitions

### 11.1 Definition of Incisional hernia

Definition and classification by European Hernia Society of Incisional hernia will be used.

In the European Hernia Society (EHS) IH classification the abdomen is divided into a midline zone and a lateral zone. Borders for the midline area are cranially the xyphoid, caudally the pubic bone and laterally the lateral margin of the rectal sheath.

PREEMER TRIAL 21

E H S			
Incisional Hernia Classification			
Midline	subxiphoidal	M1	
	epigastric	M2	
	umbilical	M3	
	infraumbilical	M4	
	suprapubic	M5	
Lateral	subcostal	L1	
	flank	L2	
	iliac	L3	
	lumbar	L4	
Recurrent incisional hernia?		Yes  No 	
length: cm		width: cm	
Width cm	W1 <4cm 	W2 ≥4-10cm 	W3 ≥10cm 

EHS classification for incisional abdominal wall hernias. (46)

Midline Incisional Hernias are divided into the following subgroups M1–M5:

[figure not shown]
M1: subxiphoidal (from the xiphoid till 3 cm caudally)

M2: epigastric (from 3 cm below the xiphoid till 3 cm above the umbilicus),

M3: umbilical (from 3 cm above till 3 cm below the umbilicus),

M4: infraumbilical (from 3 cm below the umbilicus till 3 cm above the

pubis) M5: suprapubic (from the pubic bone till 3 cm cranially).

EHS classification: zones of midline hernias.

## 11.2 Comprehensive Complication Index

All events should be classified according to the Comprehensive Complication Index.

## 11.3 Definition of Infection

CDC definition of surgical site infection for incisional site infection will be used.

Category	Criteria
Superficial incisional SSI	
Infection occurs within 30 days after the operative procedure (where day 1= the procedure date)
 
AND
 
Involves only skin and subcutaneous tissue of the incision
 
AND
 
Patient has at least one of the following:
 

purulent drainage from the superficial incision

organisms isolated from an aseptically obtained culture from the superficial incision or subcutaneous tissue

superficial incision that is deliberately opened by a surgeon, attending physician, or other designee and is culture positive or not cultured

 
AND
 
Patient has at least one of the following signs or symptoms: pain or tenderness; localized swelling; erythema; or heat. A culture negative finding does not meet this criterion
 

diagnosis of a superficial incisional SSI by the surgeon or attending physician or other designee

Deep incisional SSI	
Infection occurs within 30 or 90 days after the operative procedure (where day 1= the procedure date)
 
AND
 
Involves the deep soft tissues of the incision (eg. fascial and muscle layers)
 
AND
 
Patient has at least one of the following:
 

purulent drainage from the deep incision

a deep incision that spontaneously dehiscs or is deliberately opened or aspirated by a surgeon, attending physician or other designee and is culture positive or not cultured

 
AND
 
Patient has at least one of the following signs or symptoms: fever (<math>>38^{\circ}\text{C}</math>); localized pain or tenderness. A culture negative finding does not meet this criterion
 

an abscess or other evidence of infection involving the deep incision that is detected on gross anatomical or histopathologic exam or imaging test

Organ/space SSI	
Infection occurs within 30 or 90 days after the operative procedure (where day 1= the procedure date)
 
AND
 
Infection involves any part of the body deeper than the fascial/muscle layers, which is opened or manipulated during the operative procedure
 
AND
 
Patient has at least one of the following:
 

purulent drainage from a drain that is placed into the organ/space (eg. closed suction drainage system, open drain, T-tube drain, CT-guided drainage)

organisms isolated from an aseptically obtained culture of fluid or tissue in the organ/space

an abscess or other evidence of infection involving the organ/space that is detected on gross anatomical or histopathologic exam, or imaging test

 
AND
 
Meets at least one criterion for a specific organ/space infection site

## 11.4 Activities Assessment Scale

A Finnish translation of Activities Assessment Scale will be used (47).

Kuinka vaikeaksi olet kokenut seuraavat toimet viimeisimmän vuorokauden (24h) aikana?	Ei lainkaan vaikeaksi	Jonkin verran vaikeaksi	Melko vaikeaksi	Hyvin vaikeaksi	Mahdottomaksi	En ole tehnyt tästä viimeisen vuorokauden aikana muusta syystä
Paikoillaan makaaminen	1	2	3	4	5	6
Istuminen	1	2	3	4	5	6

Asettuminen makuulle/istuallseen	1	2	3	4	5	6
Kurkottelu tai venyttely	1	2	3	4	5	6
1-2 kg nostaminen	1	2	3	4	5	6
Sisätiloissa liikkuminen	1	2	3	4	5	6
Portaiden kiipeäminen	1	2	3	4	5	6
Liikkuminen ulkona tai töissä						
Paikoillaan olo, esimerkiksi televisiota tai tietokonetta katsoen, lukien tai puhelimessa puhuen	1	2	3	4	5	6
Kevyet askareet, esimerkiksi kevyet kotityöt, kyläily	1	2	3	4	5	6
Kohtalaisen raskaat askareet, esimerkiksi pihatyöt, lumityöt, reipas kävely, siivous	1	2	3	4	5	6
Raskas fyysisen aktiivisuus, kuten urheilu, kuntosaliharjoit telu, painavien taakkojen nostelu, raskas työ	1	2	3	4	5	6
Seksuaalinen kanssakäyminen	1	2	3	4	5	6

11.5 Promis

A Finnish translation of Promis-questionnaire will be used to evaluate the likelihood of incisional hernia(48).

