**PROMIS – kysely arpityräriskin arvioimiseksi**

1. Uskotko, että Sinulla voi olla

arpityrä?

Kyllä

Ei

2. Tunnetko kipua arvessa?

PREEMER TRIAL 24

Kyllä

Ei

3. Onko arvessa pullotusta tai pattia?

Kyllä

Ei

4. Näkyykö arvessa pullostusta tai pattia?

Kyllä

Ei

5. Painosi?

\_\_\_\_\_ kg

6. Pituutesi?

\_\_\_\_\_ cm

7. Tupakoitko, tai oletko koskaan tupakoinut

päivittäin?

Kyllä

Ei

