## 12. Schedule of Events

Schedule of Events	Baseline	Procedure	Discharge	30 days + 7 days	2 year ± 30 days	5 years ± 30 days	Unscheduled Visit
Informed Consent	X						
Demographics and medical history	X						
Risk analysis for hernia	X						
QoL (RAND-36, AAS, PROMIS)			X	X	X	X	

Procedure details		X					
Clinical evaluation	X		X	X	X	X	X
Ultrasound findings					X	(X*)	(X)
Protocol Deviation	X*	X*	X*	X*	X*	X*	X*
Complications		X*	X*	X*	X*	X*	X*
Study Closure Form						X**	

\*Complete if applicable

\*\*Complete when lost to follow-up, consent withdrawal or subject has completed all study related visits.

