#### 13.1 Subject lost to Follow-up

The investigator will attempt to contact the subject at least three times prior to designating them as lost to follow-up. The patient who may hesitate to come to follow-up visit, are asked to return the PROMIS questionnaire to estimate the risk of incisional hernia (48).

The investigator will

document the date and type of attempted communication. If a subject cannot be reached during the visit window, a missed visit will be recorded. Each patient in the trial will be invited for every follow-up visit according to schedule until he/she withdraws.

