### 19.3 Endpoint analysis

All analyses will be performed primarily according to modified intention to treat (ITT) principle.

Patients who fulfill exclusion criteria intraoperatively (after randomization) will not be included in the analyses. Per protocol analyses will be used as safeguard against the risk of falsely claiming

PREEMER TRIAL 30

equality/superiority. The primary endpoint will be the incidence difference of IHs with 95% confidence interval between the study groups during 2-years follow up. Secondary outcomes are

listed previously. The primary endpoint as well as other categorical data will be analyzed by the  $\chi^2$ - test or Fisher's exact test. Student's t-test or Welch test will be used for continuous variable, the

latter if assumption of homogenous variances does not hold. The incidence of hernia will also be

analyzed using Kaplan-Meier analysis.

The linear mixed model (LMM) or generalized linear mixed model (GLMM) will be used for repeatedly measured data, the previous for continuous data and latter for categorical data. Multiple imputations of missing outcome data will be used for sensitivity analyses.

Prospectively

planned subgroup analyses are as follows: BMI>30, previous hernia and contamination class 4.

However, sample size calculation is done only for the primary end point and subgroup analyses are hypothesis generating only. The statistical programs SPSS (IBM Corp.

Released 2016. IBM SPSS

Statistics for Windows, Version 24.0. Armonk, NY: IBM Corp) and SAS (version 9.4, SAS Institute Inc., Cary, NC, USA) will be used for the analyses.

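### PROMIS is listed as a quality-of-life endpoint, but the protocol's own definition and form make it a hernia-likelihood questionnaire

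*Protocol*

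**What the plan says.** Six places in the protocol class PROMIS as a quality-of-life instrument:

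- the synopsis (section 1), in the secondary endpoints;
- the synopsis again, in the data-collection entry;
- section 4: "Quality of life will be measured using RAND-36, Activities Assessment Scale (AAS) and PROMIS";
- section 6.2, as a secondary endpoint: "Quality of life (RAND-36, AAS, PROMIS) within 30 days, 2 and 5 years from surgery";
- the 30-day visit list in the Data Collection section;
- the schedule in section 12, in a row labelled "QoL (RAND-36, AAS, PROMIS").

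Three places describe something else:

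- Section 11.5: "A Finnish translation of Promis-questionnaire will be used to evaluate the likelihood of incisional hernia".
- The form printed below it is headed "PROMIS – kysely arpityräriskin arvioimiseksi", which is Finnish for a questionnaire to assess incisional hernia risk.
- Section 13.1, on loss to follow-up, says that patients who hesitate to attend "are asked to return the PROMIS questionnaire to estimate the risk of incisional hernia".

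On missing outcomes, section 19.3 says: "Multiple imputations of missing outcome data will be used for sensitivity analyses". It does not mention PROMIS.

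**The concern.** One instrument has two incompatible descriptions, and one of them sits in the endpoint list. A statistical analysis plan that follows section 6.2 would compare PROMIS between arms under the quality-of-life heading. Readers would then take any difference as a patient benefit distinct from hernia prevention, although most of the informative items ask whether the patient thinks a hernia or bulge is there. What is at stake is how one secondary result is interpreted. The validity of the primary comparison is not in question.

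**Working it through.** **1. Item content against the label.** The seven items on the printed form fall into three groups:

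| Items | Subject | Number |
|---|---|---|
| Belief that a hernia is present; bulge or lump in the scar; bulge or lump visible | Suspected hernia | 3 |
| Pain in the scar | Symptom | 1 |
| Weight; height; daily smoking, now or ever | Risk factors | 3 |

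Only scar pain comes near health-related quality of life. The protocol defines no quality-of-life score for the form. RAND-36 and AAS have no such conflict.

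**2. What a between-arm difference would mean.** Section 19.1 plans on hernia rates of 25% (control) and 10% (mesh), a difference of 15 percentage points. Suppose a suspected-hernia item is answered yes with probability *se* when a hernia is present and 1 − *sp* when it is absent, and that both are the same in the two blinded arms. The expected proportion answering yes in an arm with hernia rate *p* is

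p × se + (1 − p) × (1 − sp).

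Subtracting one arm from the other gives

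(0.25 − 0.10) × (se + sp − 1) = 15 points × (se + sp − 1).

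The protocol gives neither *se* nor *sp*. For any item that carries information, the result lies between 0 points (uninformative) and 15 points (perfect). On this assumption the whole difference is the primary-endpoint difference, attenuated. No separate quality-of-life effect enters it.

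**3. The risk-factor items.** Allocation is randomised and stratified by BMI below or above 30 (section 19.2). Weight, height and smoking should not differ systematically between arms. They add no hernia signal and no treatment benefit to a between-arm comparison.

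**4. Reach into the primary analysis.** The table in section 6.1 takes only clinical examination and imaging as inputs, so PROMIS does not enter the primary endpoint. The planned sample size reproduces without reference to PROMIS:

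(1.960 + 0.842)² × (0.25 × 0.75 + 0.10 × 0.90) / 0.15² = 96.8, rounded up to 97 per group.

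97 / 0.80 = 121.25, rounded up to 122 per group, 244 in total.

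Reclassifying PROMIS changes none of these figures.

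**5. Ceiling on the optional use for missing outcomes.** Planned dropout is 0.20 × 122 = 24.4 per arm, or 0.20 × 244 = 48.8 overall. This is an upper bound on the patients whose missing 2-year outcome PROMIS could inform. Under section 13 withdrawn patients have no further study follow-up, and patients who cannot be reached or have died return no form. No return rate is given.

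**The case against.** The strongest reply is that the quality-of-life listing is a convenient grouping of questionnaires. The only stated use of the form, in sections 11.5 and 13.1, is hernia likelihood, and section 19.3 names no PROMIS comparison. Section 19.1 makes all secondary outcomes hypothesis generating, and RAND-36 and AAS remain as genuine quality-of-life measures. This limits the consequence, and that part stands. It does not remove the contradiction, because section 6.2 is an endpoint definition and section 4 says outright that quality of life is measured with PROMIS.

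Three stronger readings are tempting and should not be drawn:

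- *Hernia is counted twice.* No composite or combined quality-of-life score containing PROMIS is specified, and PROMIS does not feed the primary endpoint. The risk is that the same finding is reported again under another name.
- *The form's value for missing outcomes is ignored.* Section 13.1 gives the returned forms a purpose. Which variables enter an imputation model is commonly settled in a statistical analysis plan, which is not at hand, so silence in section 19.3 is not a defect.
- *PROMIS is the only outcome information on non-attenders.* The Study Plan section allows registers to be used for operations done outside the study sites and asks patients to make contact on any suspicion of hernia. The schedule provides unscheduled visits with clinical evaluation and ultrasound. Registers would miss unrepaired hernias, but PROMIS is not the sole source. Some patients who hesitate will also attend after all.

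**Conclusion.** The protocol contradicts itself on what PROMIS measures, and the conflict reaches a listed secondary endpoint. Following section 6.2 as written would report suspicion of hernia as quality of life. The severity is minor: the effect is confined to the interpretation of one hypothesis-generating endpoint.

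That a PROMIS difference would largely restate the primary endpoint rests on two assumptions: mesh lowers hernia incidence, and patients in the two arms answer the hernia and bulge items alike for a given hernia status. The scar-pain item is the exception, since pain could differ between arms for reasons other than hernia. The figure of about 24 per arm is a ceiling on an optional use of the data and does not measure the size of the inconsistency.

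**What to change.** Remove PROMIS from the quality-of-life endpoint and lists in all six places: both synopsis entries, section 4, section 6.2, the 30-day visit list and the schedule in section 12. Keep RAND-36 and AAS as the quality-of-life measures. Give PROMIS its own schedule row at the same visits, and report it separately as patient-reported suspicion of hernia.

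Optionally, add a sentence to section 19.3 or the statistical analysis plan that PROMIS answers, including those returned under section 13.1, serve as auxiliary variables in the planned multiple-imputation sensitivity analysis of the 2-year hernia outcome.

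No new data, visits or patients are needed. The change does alter a listed secondary endpoint, so it should be made as a documented amendment before results by arm are seen.
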